10.3.1 Primary endpoint

The primary endpoint:

- Height velocity (cm/year) during the first 52 weeks will be derived from height measurements taken at baseline and the week 52 visit (landmark visit) in the following way: $HV = (\text{height at 52 weeks visit} - \text{height at baseline}) / (\text{time from baseline to 52 weeks visit in years})$.

Annualized HV at the intermediate visits: Week 13, 26 and 39, will be derived analogously to the week 52 HV: $HV = (\text{height at } j \text{ weeks visit} - \text{height at baseline}) / (\text{time from baseline to } j \text{ weeks visit in years})$, $j=13, 26, 39$.

Primary estimand (FDA and PMDA)

The primary objective is to compare the effect of somapacitan vs Norditropin® on longitudinal growth in children with GHD and the primary analysis of the primary endpoint will be used for confirming non-inferiority of somapacitan compared to Norditropin® based on the primary estimand Section [4.2.1](#)

The primary analysis of the primary endpoint is based on the FAS. Subjects with no landmark visit data will have landmark visit data imputed based on available landmark visit data from retrieved subjects from the same treatment arm using Multiple Imputations (MI). If number of retrieved subjects per arm is less than 20 for at least one of the treatment arms (based on the assumptions: ~6 from the largest treatment arm), MI will be done in a model using all landmark visit data from the same treatment arm but with different mean parameters for the two status subgroups: (stayed on randomised treatment at the landmark visit; combined group of withdrawals and retrieved subjects), but same variance.

The analysis will be implemented as follows:

In the first step, missing week 52 values are imputed using a Markov Chain Monte Carlo method. This imputation is done for each treatment group separately and 100 copies of the dataset will be generated (seed=5297). The number of copies can be increased if the estimation process does not result in robust estimates.

For each of the complete data sets, HV at week 52 is analysed using an analysis of covariance model with treatment, gender, age group, region, GH peak group and gender by age group by region interaction term as factors, and baseline height as covariate.

The estimates and standard deviations for the 100 data sets are pooled to one estimate and associated standard deviation using Rubin's formula:

$$m_{MI} = \frac{1}{100} \sum_{i=1}^{100} m_i, \quad SD_{MI} = \sqrt{\frac{1}{100} \sum_{i=1}^{100} SD_i^2 + \left(1 + \frac{1}{100}\right) \left(\frac{1}{100-1}\right) \sum_{i=1}^{100} (m_i - m_{MI})^2}$$

where m_i and SD_i are the estimated means and standard deviations for the 100 copies of the dataset, and m_{MI} and SD_{MI} are the pooled estimates.

From these pooled estimates the confidence interval for the treatment difference and the associated p-value will be calculated.

Non-inferiority of somapacitan will be considered confirmed if the lower boundary of the two-sided 95% confidence interval is above -1.8 cm/year or equivalent if the p-value for the one-sided test of

$H_0: D \leq -1.8$ cm/year vs $H_A: D > -1.8$ cm/year is less than 2.5 %, where D is the mean treatment difference (somapacitan – Norditropin®). If non-inferiority is confirmed, superiority will be considered confirmed if the lower boundary of the two-sided 95% confidence interval is above 0 cm/year. If superiority is confirmed, the p-value from the two-sided superiority test will also be reported.

If the actual number of retrieved subjects turns out to be 20 or more from each treatment arm (so more retrieved subjects than expected from the assumptions), it will be possible to model the mean with more parameters using height baseline value and time to last dose as covariates and then do MI within each treatment arm for the status subgroup consisting of withdrawals and retrieved subjects. The rest of the analysis procedure will be identical to the procedure stated above.

A tipping point analysis will be conducted as a sensitivity analysis for the primary analysis of the primary endpoint for the primary estimand where imputed landmark visit values will be penalized by a value $c > 0$ in the somapacitan treated arm (by subtracting c multiplied by the fraction of subjects with imputed landmark visit values in the somapacitan treated arm from the treatment difference estimate and the corresponding 95% CI). The analysis is used to investigate the robustness of the results, targeting the chosen imputation method of missing landmark data. It will be conducted by increasing c until the resulting 95% CI no longer is completely above -1.8cm/year.

Additionally, a value $b \geq 0$ will be added to the imputed landmark visit value for Norditropin® treated subjects prior to analysis, so that the tipping point analysis also can address scenarios where withdrawals from the active comparator arm achieve greater HV than the value estimated from retrieved subjects (two-dimensional tipping point analysis).

Primary estimand (EMA)

The primary analysis of the primary endpoint addressing the alternative primary estimand Section [4.2.2](#) is based on FAS but data assessed after discontinuation of randomised treatment will be disregarded in the analysis.

In order to estimate this primary estimand (hypothetical strategy) a mixed model for repeated measurements (MMRM) with an unstructured covariance matrix is conducted on HV data (annualized HV at planned visits at week 13, 26, 39 and 52) up to discontinuation of randomised treatment for each treatment arm using all randomised subjects and assuming missing at random (MAR) for both treatment arms. The MMRM will include gender, age group, region, GH peak group and gender by age group by region interaction term as factors and baseline height as a covariate, all nested within week as a factor.

From this analysis an estimate of the treatment difference at week 52 with corresponding 95% CI and p-value will be presented.

Non-inferiority of somapacitan will be considered confirmed if the lower boundary of the two-sided 95% confidence interval is above -1.8 cm/year or equivalent if the p-value for the one-sided test of

$H_0: D \leq -1.8$ cm/year vs $H_A: D > -1.8$ cm/year is less than 2.5 %, where D is the mean treatment difference (somapacitan – Norditropin[®]). If non-inferiority is confirmed, superiority will be considered confirmed if the lower boundary of the two-sided 95% confidence interval is above 0 cm/year. If superiority is confirmed, the p-value from the two-sided superiority test will also be reported.

A tipping point analysis will be conducted as a sensitivity analysis for the analysis of the primary endpoint for the primary estimand described above (hypothetical strategy). For this analysis, the missing data are expected to be mainly due to subjects that are withdrawn from the trial or discontinue randomised treatment. The sensitivity analyses described below will be used to investigate whether the results from the primary analysis are robust against departures from the assumption of MAR.

Let δ be defined as the difference between the mean of the observed data and the mean of the unobserved data $\mu_{obs} - \mu_{unobs}$, adjusted for other observed data. Under an MAR analysis, δ is assumed to be 0. Positive values of δ indicate that subjects with missing endpoint values have smaller HV than subjects with observed endpoint values. If subjects primarily withdraw or discontinue randomised treatment due to a perceived lack of efficacy then this could be the most likely direction of departure from MAR. Let f_1 and f_0 be the fractions of subjects with unobserved endpoint data in the somapacitan and Norditropin[®] arms, respectively. The sensitivity analysis is done by subtracting a quantity Δ from the treatment effect estimate under the MAR assumption, where $\Delta = f_1\delta$ if data depart from MAR in the somapacitan arm only, $\Delta = -f_0\delta$ if data depart from MAR in the Norditropin[®] arm only, and $\Delta = (f_1 - f_0)\delta$ if data depart from MAR in the same way in both arms. The calculations for the 3 scenarios will use a range of δ values increasing from 0 until the resulting 95% CI no longer is completely above -1.8cm/year for the most conservative evaluation (data depart from MAR in the somapacitan arm only) and the approximation that the standard error of the treatment difference is unaffected by the sensitivity analysis²⁵. All subjects from the FAS can be viewed as included in this analysis as subjects with missing endpoint data will be contributing to one of the fraction values f_1 and f_0 .

An analysis of the primary endpoint using the same analysis model as was used for the primary analysis under the primary estimand (hypothetical strategy) but based on PP instead of FAS will be conducted as a supplementary analysis.

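### The FDA/PMDA primary imputation has no rule for an arm with a child to impute and no retrieved child, and it leaves out covariates that the ANCOVA uses

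*Combined protocol and SAP*

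**What the plan says.** For the treatment policy estimand, section 10.3.1 starts from this principle: "Subjects with no landmark visit data will have landmark visit data imputed based on available landmark visit data from retrieved subjects", taken from the same treatment arm. If either arm has fewer than 20 retrieved children, a simpler model applies: "MI will be done in a model using all landmark visit data from the same treatment arm but with different mean parameters" for two status subgroups ("stayed on randomised treatment at the landmark visit; combined group of withdrawals and retrieved subjects") and one common variance. On mechanics: "This imputation is done for each treatment group separately and 100 copies of the dataset will be generated". The number of copies may be raised if estimates are not robust. No other flexibility is given.

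Only with 20 or more retrieved children in each arm does the plan add covariates: "it will be possible to model the mean with more parameters using height baseline value and time to last dose as covariates". The stratification factors are named in neither branch. The ANCOVA fitted to each completed data set contains "treatment, gender, age group, region, GH peak group and gender by age group by region interaction term as factors, and baseline height as covariate".

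Section 10.1 expects 5% of children to be retrieved and 5% to have no week-52 data, with the same proportions in both arms. Section 10.3 allows a more detailed SAP if needed, to be finalised before database lock. No separate SAP is among the documents reviewed.

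**The concern.** In the under-20 branch, the mean used to impute withdrawn children can be learned only from retrieved children in the same arm. If an arm has none, the data do not identify that mean. The other arm may not be used, and more imputed copies do not help. The tipping point analysis cannot stand in, because its penalty is subtracted "from the treatment difference estimate and the corresponding 95% CI", which the imputation must first produce.

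This is the analysis on which non-inferiority, and then superiority, is decided for FDA and PMDA. In the empty-arm case the written rule yields no primary result. Under section 10.3.4 the sponsor is unblinded at the interim lock, so a repair chosen after that would be post hoc. Section 10.3.2 uses the same analysis model for height SDS and HV SDS, so they share the gap if that model includes the imputation step.

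A second, smaller issue is that the imputation model omits baseline height and the strata used in the ANCOVA. Imputed values then carry noise that the analysis model would otherwise explain.

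**Working it through.** **Inputs.** N = 192 (sections 5.2 and 10.1), randomised 2:1 (section 5.1), hence 128 somapacitan and 64 Norditropin. Retrieved rate r = 5%, missing rate m = 5%, SD 3.5 cm/year, margin 1.8 cm/year, one-sided 2.5% (section 10.1). All children without week-52 data are counted as withdrawn.

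**The plan's own figures.** Expected retrieved: 0.05 × 128 = 6.4 (the plan says about 6) and 0.05 × 64 = 3.2. A two-group t-test needs 183 evaluable children for 90% power, and 183 / 0.95 = 193 against the stated 192. Power with 95% of 192 evaluable is 90.3%. The inputs are therefore read as the plan intends.

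**Which branch applies.** P(20 or more retrieved on Norditropin) = 2 × 10⁻¹¹ for Binomial(64, 0.05). Even at an assumed 20% retrieved rate, both arms reach 20 in only about 2% of trials.

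**Probability of an empty arm.** For an arm of n children, P(none retrieved and at least one to impute) = (1 − r)ⁿ − (1 − r − m)ⁿ.

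- Norditropin: 0.95⁶⁴ − 0.90⁶⁴ = 3.75% − 0.12% = 3.63%.
- Somapacitan: 0.95¹²⁸ − 0.90¹²⁸ = 0.14%.
- Either arm: 1 − (1 − 0.0363)(1 − 0.0014) = 3.77%. Simulation gave 3.80%.

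For neither arm having a retrieved child while someone must be imputed, the same formula applies with n = 192. Rates other than 5%/5% are assumptions.

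| Retrieved / missing | Either arm empty | Neither arm has a retrieved child |
|---|---|---|
| 5% / 5% (plan) | 3.8% | 0.005% |
| 3% / 3% | 14.1% | 0.29% |
| 2% / 2% | 25.7% | 2.0% |
| 1% / 1% | 40.2% | 12.5% |
| 2% / 8% | 32.8% | – |
| 8% / 2% | 0.37% | – |

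At the plan's rates, about 17% of trials have an arm with someone to impute and at most one retrieved child. Thin support is therefore more common than the empty case alone.

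**Does the choice of repair matter?** Take trials in which Norditropin has a child to impute and none retrieved, and assume discontinuers grow 2 cm/year less in both arms (6,000 simulated trials). With all data observed the mean difference is −0.091 cm/year. A status effect common to both arms gives −0.090. Imputing from the on-treatment model gives −0.198.

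**Omitted covariates.** Simulation: 10,000 trials per scenario, 100 imputations, total SD 3.5, 5% retrieved and 5% missing, ANCOVA with main effects only, assumed 15% region share. Mean SE of the treatment difference in trials where the written model can be fitted:

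| Assumed R² | As written | With covariates | Increase |
|---|---|---|---|
| 0.10 | 0.5599 | 0.5571 | 0.5% |
| 0.20 | 0.5352 | 0.5247 | 2.0% |
| 0.40 | 0.4829 | 0.4546 | 6.2% |

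A simpler one-covariate simulation agreed: 0.530 against 0.517 at R² 0.20, and 0.478 against 0.447 at R² 0.40. There was no material bias, and non-inferiority power was about 1.5 points lower without the covariate.

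**The case against.** The strongest case on the other side is that the gap is rare and easy to close. At the plan's rates, which section 10.1 bases on phase 2 data, the rule works in about 96% of trials. Sections 8 and 8.1 press sites to bring discontinued children back for visit 7, which favours retrieval over missingness; at 8% / 2% the probability is 0.4%. A SAP could supply the rule before lock, and section 7.4 keeps the sponsor staff who interpret data blinded until then. An MCMC run with a proper prior would also produce numbers.

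The rarity stands, and so does the possibility of a SAP rule. But that SAP is optional and not among the documents. The 5%/5% expectation should already reflect the efforts to retain children to visit 7. The plan specifies no prior, and with one the imputed values would come from the prior rather than from children.

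On the covariates, the objection is that no R² is documented, the loss is small and conservative, and a main-effects imputation model still lacks the ANCOVA's three-way interaction. All of that is true. It makes this the lesser part; it does not remove a gain available from data already collected.

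A last objection is that borrowing a status effect across arms could favour somapacitan. It could. If only somapacitan discontinuers grow 2 cm/year less (assumed) and Norditropin has none retrieved, the difference shifts by about 0.11 cm/year towards somapacitan. One-sided type I error is then about 4% within those rare trials, but 2.3% overall.

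**Conclusion.** The concern holds and should be fixed. The under-20 branch is practically certain. Within it, an arm with a withdrawn child and no retrieved child leaves the FDA/PMDA primary analysis undefined. The probability is 3.8% at the plan's 5%/5% and 128:64; it rises quickly if fewer children are retrieved and falls if more are. Omitting baseline height and the strata is a minor loss of precision whose size depends on an R² the documents do not give. Its effect on the treatment difference is small, since only about 10 children (0.05 × 192 = 9.6) are imputed. None of this implies that the trial misses its stated 90% power.

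**What to change.** For the under-20 branch, write into the protocol or a SAP finalised before database lock:

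1. Impute week-52 HV within arm from status (on treatment; withdrawn or retrieved), baseline height, gender, age group, region and GH peak group. Use main effects, slopes common to the two status groups and one variance. Drop a factor from an arm's model if it has only one level among that arm's children with week-52 data.
2. If an arm has at least one withdrawn child to impute and no retrieved child, fit the same model to both arms together, with arm intercepts and one status effect common to the arms.
3. If neither arm has a retrieved child, use each arm's on-treatment model and present it with the planned two-dimensional tipping point analysis.
4. Apply the same rule to height SDS and HV SDS, with the matching baseline SDS in place of baseline height.

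In simulation at R² 0.20, the revised rule gave a mean estimate of −0.003 at a true difference of 0, 95.2% coverage, and a one-sided type I error at −1.8 of 2.3% (Monte Carlo SE 0.15 points).

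The cost is wording and a slightly larger model, with no new data. Step 2 gives up the same-arm principle, but only where no same-arm estimate exists. If discontinuers in one arm only grew 2 cm/year less (assumed), the difference in trials where Norditropin is the empty arm would be off by 2 × 3.48 / 64 = 0.109 cm/year, in either direction. Here 3.48 is the expected number missing given none retrieved and at least one missing. Where only Norditropin discontinuers differ, that averages 0.0363 × 0.109 = 0.004 cm/year over all trials. The planned penalties c and b probe both directions; b was added "so that the tipping point analysis also can address scenarios where withdrawals from the active comparator arm achieve greater HV". The covariate slopes would be learned mostly from on-treatment children.

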3.2 Background

3.2.1 Growth hormone deficiency

GH is essential for normal longitudinal growth in children and acts partly by direct action on the growth plates and partly by stimulation of insulin-like growth factor-I (IGF-I) release². Besides, the importance of GH and IGF-I for facilitating growth in children, both proteins are also involved in various metabolic processes in children as well as in adults³.

Rapid proteolysis and ligand-receptor internalisation result in a short half-life for human growth hormone (hGH).

Consequently, hGH is given as daily injections. Children and adults with GHD currently require many years or lifelong treatment with a daily s.c injection regimen. Studies investigating treatment adherence have shown that approximately one-fourth of children on GH treatment misses more than two of the seven injections per week⁴⁻⁶.

GHD may occur as an isolated hormonal deficiency or in combination with multiple pituitary hormone deficiencies. It may result from congenital, genetic, acquired (by tumours in the central nervous system, cranial irradiation, head trauma or other organic causes) or idiopathic causes. Idiopathic GHD is the most common form, accounting for approximately 75% of diagnosed patients⁷.

GHD in children is characterised by a reduced HV and a markedly reduced final adult height compared to the predicted height based on mid-parental height. Normal growth can be restored with GH replacement therapy⁷. The treatment for GHD in children is the same whether the cause is congenital, genetic, acquired or idiopathic⁷⁻⁹. GHD may be present already at birth but is generally first discovered within the first years of childhood.

Experience gained during the last 15-20 years shows that GH treatment is also effective in restoring normal growth in children with other forms of growth retardation, including Turner and Noonan

syndromes, children with chronic renal failure and children born small for gestational age with insufficient catch up growth [9,10](#).

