5.1 Overall design

A randomised open-labelled two arm (somapacitan and Norditropin[®]) trial designed to compare the effect and safety of once weekly dosing of somapacitan with daily dosing of Norditropin[®] after 52 weeks in children with growth hormone deficiency followed by a 3 year single-arm extension period with once weekly dosing of somapacitan to evaluate safety. The randomisation will be stratified by region (Japan versus rest-of-the-world) as well as age group (< 6 versus ≥ 6 years at randomisation), gender (boys versus girls) and growth hormone peak level (< 7.0 versus ≥ 7.0 ng/ml) to ensure equal distribution of these factor levels across treatments.

The total trial duration for a subject will be 4 years.

Eligible subjects will be randomised in a 2:1 manner to receive either somapacitan (2 out of 3 subjects) or Norditropin[®] (1 out of 3 subjects).

The follow-up period is a minimum of 30 days.

[figure not shown]

Figure 1 Trial design

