10.1 Sample size determination

The sample size calculation is based on the primary estimand described in Section [4.2](#).

It is expected based on phase 2 trial data (NN8640-4172) that the proportion of subjects with no landmark visit data or who discontinued randomised treatment before landmark visit is 10% with similar withdrawal reasons in the two treatment arms (5% discontinuing randomised treatment but have landmark visit data and 5% withdrawn /lost to follow up with no landmark visit data). It is expected that subjects discontinuing their randomised treatment will start on ancillary treatment, if no medical reasons prohibits this. The term “retrieved subjects” will be used in this section as a short form for “subjects discontinuing randomised treatment but have landmark visit data”.

Assuming the same proportions of subjects with no landmark visit and retrieved subjects in the two arms leads to the following sample size calculation.

Primary estimand (FDA and PMDA)

The sample size is determined using a non-inferiority margin of 1.8 cm/year and a one sided two-group t-test with a significance level of 2.5% for a 2:1 randomisation ratio between somapacitan and Norditropin®.

As trial results from trials allowing ancillary therapy or having retrieved landmark data included in the analysis are limited, a conservative standard deviation for HV at week 52 was chosen (SD=3.5cm/year) and the different scenarios giving 90% power for the primary analysis are presented in the table below under the assumption of a true difference in annualized HV of 0 cm/year between the two treatment arms and no true difference in annualized HV between retrieved subjects and subjects staying on randomised treatment at landmark visit.

Table 3 Sample size for various standard deviations

SD	3.0 cm/year	3.25 cm/year	3.5 cm/year	3.75 cm/year
Primary estimand	144	171	192	219
(Treatment policy strategy)				

The SD candidates are based on reported SD values from clinical trials [21-23](#). For sensitivity analysis a tipping point analysis is planned and based on a penalty for imputed values in the somapacitan arm of 1.8 cm/year this gives a power of 87% (adjusted treatment effect: $0.9*0 - 0.05*1.8 = -0.09$), under the assumption of 5% of subjects not having landmark visit data (corresponding to an analysis that performs an imputation under the non-inferiority null method).²⁴

Primary estimand (EMA)

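### The FDA/PMDA ANCOVA assumes one residual variance for both arms under 2:1 allocation, so its interval holds the stated one-sided 2.5% error only if the arms have equal SDs.

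*Combined protocol and SAP*

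**What the plan says.** Section 5.1: "Eligible subjects will be randomised in a 2:1 manner to receive either somapacitan (2 out of 3 subjects"), with the remaining third going to Norditropin. At 192 subjects this is 128 and 64.

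Section 10.1 plans with one SD for both arms, using "a one sided two-group t-test with a significance level of 2.5% for a 2:1 randomisation ratio" and "a conservative standard deviation for HV at week 52 was chosen (SD=3.5cm/year").

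Section 10.3.1, FDA/PMDA estimand: missing week 52 values are imputed separately by arm. In each of the 100 completed data sets "HV at week 52 is analysed using an analysis of covariance model with treatment, gender, age group, region, GH peak group", an interaction term and baseline height. Each standard error then enters Rubin's formula. No arm-specific residual variance, robust standard error or unequal-variance sensitivity analysis is mentioned. The equal-variance remark in the imputation paragraph concerns two status subgroups within an arm, not the two arms.

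Section 10.3.1, EMA estimand: a "mixed model for repeated measurements (MMRM) with an unstructured covariance matrix is conducted on HV data" over the four visits. The sentence goes on to refer to each treatment arm, and the list of model terms contains no treatment term. The MMRM for the pharmacodynamic endpoints in section 10.3.2 does list treatment.

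For both estimands the lower limit of the two-sided 95% interval decides non-inferiority (-1.8 cm/year) and then superiority (0 cm/year).

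**The concern.** With a common variance and 2:1 allocation, the pooled residual variance takes about two thirds of its weight from the larger arm. The variance of the treatment difference has the opposite make-up: with equal SDs, two thirds of it comes from the smaller Norditropin arm. When the SDs are equal the two agree. When they differ, the standard error is too small if Norditropin is the more variable arm and too large if somapacitan is. In the first case the one-sided error exceeds 2.5% for both decisions. In the second, power is given away.

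The planned sensitivity analyses would not reveal this, because they address missing data. In the FDA/PMDA tipping point analysis, the somapacitan penalty moves the estimate and its interval by a constant, and the shift applied to imputed Norditropin values goes back into the same ANCOVA. The EMA version takes the standard error as unaffected.

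**Working it through.** **Inputs.** From section 10.1: margin 1.8 cm/year, SD 3.5 cm/year, one-sided 2.5%, 90% power, true difference 0, 5% without landmark data. From section 5.1: 2:1 allocation. The SD ratio r = Norditropin SD / somapacitan SD is not in the documents. It is an assumption, shown as a range.

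**The plan's own figure.** The normal approximation gives 60 Norditropin subjects and 180 in total. The noncentral t gives 183 (122 and 61). 183/0.95 = 192.6, against 192 stated, so the sample size reproduces under a single common SD.

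**Formulas.** With n1 = 128 and n0 = 64:

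- pooled variance: sp² = [(n1-1)s1² + (n0-1)s0²]/(n1+n0-2)
- standard error used: sp·√(1/n1 + 1/n0)
- correct standard error: √(s1²/n1 + s0²/n0)
- one-sided error ≈ 1 - Φ(t × SE used / SE correct), with t = 1.97 on 190 df

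Holding sp at 3.5, the standard error used is 3.5 × √(1/128 + 1/64) = 0.536, so the half-width is 1.057 cm/year whatever r is.

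**Worked case, r = 1.25.** s1 = 3.5 × √[190/(127 + 63 × 1.5625)] = 3.21 and s0 = 4.02. The correct standard error is √(3.21²/128 + 4.02²/64) = 0.577. The ratio is 0.536/0.577 = 0.929, and 1 - Φ(1.97 × 0.929) = 0.033.

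| r | s1 | s0 | correct SE | SE used / correct | correct half-width | one-sided error |
|---|---|---|---|---|---|---|
| 0.8 | 3.73 | 2.98 | 0.498 | 1.076 | 0.982 | 1.7% |
| 1.0 | 3.50 | 3.50 | 0.536 | 1.000 | 1.057 | 2.4% |
| 1.1 | 3.38 | 3.72 | 0.553 | 0.969 | 1.091 | 2.8% |
| 1.25 | 3.21 | 4.02 | 0.577 | 0.929 | 1.138 | 3.3% |
| 1.5 | 2.94 | 4.41 | 0.610 | 0.878 | 1.203 | 4.2% |

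The 2.4% at r = 1 comes from pairing a t critical value with a normal tail. The exact value is 2.5%.

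**Check by simulation, two groups.** At 122 and 61 subjects (95% of 128 and 64), two separate simulations of the pooled t-test gave 1.7-1.8%, 2.5%, 2.8%, 3.3-3.4% and 3.9% at r = 0.8, 1.0, 1.1, 1.25 and 1.4. The unequal-variance (Welch) t-test gave 2.4-2.5% throughout. Power went from 90.3% to 90.1% at r = 1, and from 91.8% to 93.8% at r = 0.8.

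**Check by simulation, ANCOVA.** This used the protocol's covariates with assumed prevalences, complete data and 128:64, at the -1.8 boundary, with 12,000 runs per ratio (Monte Carlo standard error about 0.14 points). Pooled against HC2 robust standard error:

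- r = 0.8: 1.7% against 2.4%
- r = 1.0: 2.4% against 2.4%
- r = 1.25: 3.1% against 2.2%
- r = 1.5: 4.3% against 2.6%

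A separate ANCOVA simulation put the HC2 error at 2.4-2.8%. None of these runs includes the imputation step or the MMRM.

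**The case against.** A reader might infer more than the documents support, in two ways.

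**That both primary models pool.** One matrix shared by both arms is the usual reading of the EMA model. But the sentence refers to each treatment arm and the term list omits treatment, so a fit by arm with separate matrices is not excluded. What stands for that model is that its covariance grouping is unspecified.

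**That Norditropin will be the more variable arm.** Section 3.2.1 reports that "approximately one-fourth of children on GH treatment misses more than two of the seven injections per week", and sections 3.1 and 3.2.2 hope for better adherence with weekly dosing. The adherence figure comes from cited studies, not from trial arms with diaries and pen counts, and sections 3.1 and 3.2.2 state a possibility and an aim, not an expectation. Poor adherence may also lower the mean without widening the spread.

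Other figures do not settle the direction. Section 5.4 gives SDs of 1.09 at a mean of 2.93 cm/year and 3.09 at 11.97, a slope of 2.00/9.04 = 0.22 per cm/year. If SD followed the mean, the higher somapacitan mean reported from phase 2 (11.5 against 9.8) would make somapacitan the more variable arm and the interval conservative. At the -1.8 boundary, 1.8 × 0.22 = 0.40 gives r of 3.5/3.10 = 1.13 to 3.09/2.69 = 1.15. By interpolation in the simulated errors that is about 2.9-3.0%. At the superiority null r would be about 1. This compares baseline with treated growth in one arm, so it is only indicative.

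It is also fair that a common-variance ANCOVA is conventional and matches the planning test, and that the interval changes little: 0.03 cm/year in half-width at r = 1.1 and 0.08 at 1.25, against a margin of 1.8. A decision changes only if the lower limit falls that close to -1.8 or 0. All of this limits the weight of the point. It does not show that the 2.5% is held when the SDs differ.

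**Conclusion.** The point holds for the FDA/PMDA ANCOVA as written: the stated one-sided 2.5% depends on equal SDs, and nothing in the plan checks or relaxes that. The documents do not show that the SDs differ, or in which direction, so they do not support a claim that the trial's error rate is inflated. Over the assumed ratios from 0.8 to 1.25 the error runs from about 1.7% to 3.4%. These figures rest on a pooled SD of 3.5, 2:1 allocation and complete or 95% complete data. For the EMA MMRM the supportable point is that the text does not settle whether the matrix is shared. This is a cheap improvement, not a defect that undermines the design.

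**What to change.** In section 10.3.1 or the SAP, before the interim database lock:

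- **ANCOVA.** In each imputed data set, compute the standard error of the treatment difference with a small-sample heteroscedasticity-robust estimator, then apply Rubin's formula. HC2 is the natural choice because it was checked with the protocol's covariates. Arm-specific residual variances are an acceptable alternative, but the plan should name one.
- **MMRM.** State the treatment-by-week term. Fit the unstructured covariance by treatment arm with Satterthwaite or Kenward-Roger degrees of freedom. Prespecify a common matrix as the fallback if the model does not converge. This is secondary to the ANCOVA change.

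The cost is one model option per analysis and about 0.2-0.3 percentage points of power if the SDs are equal (about 1 to 1.5 points with the more conservative HC3). If Norditropin is the more variable arm, power is lower but correctly stated: at r = 1.25, 87.5% instead of 90.1% (128:64, complete data). If somapacitan is the more variable arm, power is gained.
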